9.4.3 Handling of missing values/censoring/discontinuations

For efficacy variables based on response (e.g. IGA response, EASI50 response, EASI75 response) missing data will be handled as follows:

1. Subjects with use of confounding therapy as adjudicated will be considered as non-responders after application of the therapy.

2. Subjects who discontinue study treatment permanently or discontinue the study due to lack of efficacy or due to adverse event will be considered as non-responder after discontinuation.

Confidential

3. For subjects who discontinue study or treatment due to other reasons than above or have missing data due to other reasons, missing-at-random will be assumed. The estimates for the logits of the response probabilities as well as the corresponding covariance matrix will be derived applying multiple imputation (MI). The MI model will include IGA categories from all visits from randomization up to Week 16 as well as all EASI score at baseline and absolute change from baseline EASI score for all visits from baseline up to Week 16. For each imputed dataset the logistic regression described in Section 9.4.1 will be performed and results combined for estimation.

For the estimation of the IGA response rates at Week 16 for each treatment group, the estimate for subjects in (3) above will be combined with the non-responders in (1) and (2) above. These combined estimates will be used as input for the MCP-Mod analysis.

If a baseline value is missing, it will be imputed by the mean of the respective treatment group in the respective randomization stratum.

If not stated otherwise, for the secondary

the observed values will be

used for summary statistics, missing values will not be imputed. When doing inference, any missing data will be handled by the respective MMRM model.

For any percent change from baseline analysis, any baseline values equal to zero will be ignored. The total number of zero baseline values will be provided as additional information.

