# 2.5.3 Handling of missing values/censoring/discontinuations

Where data for IGA response are missing, either because the IGA was not recorded or because the IGA response was set to missing as part of the handling of intercurrent events, the IGA score will be imputed using multiple impuation methods and the IGA response derived from this imputed IGA score.

The multiple imputation model will include IGA categories from all visits from randomization up to Week 16.

For the estimation of the IGA response rates at Week 16 for each treatment group, each imputed dataset for subjects with missing data above will be combined with the non-missing responses for subjects without missing data. For each imputed dataset the logistic regression will be performed and results combined for estimation.

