# 2.6.8 Handling of missing values/censoring/discontinuations

Where data for a binary response endpoint are are missing, either because the underlying score was not recorded or because the response was set to missing as part of the handling of intercurrent events, the underlying score (IGA, or EASI) will be imputed using multiple impuation methods and the response derived from this imputed score.

The multiple imputation model will include scores from all visits from randomization up to the time point of imputation.

For endpoints that are analyzed as continuous variables (for example EASI score % change from baseline), missing values will not be imputed. In this cases the MMRM analysis approach is used to handle the missing data.

If a baseline value is missing and required to derive an endpoint, the baseline value will be imputed by the mean of the respective treatment group in the respective randomization stratum.

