## 5.2.3 Multiple imputations for response variables

Where multiple imputation is specified, the missing data will be imputed based on the individual treatment arm information.

Multiple imputation (MI) is a simulation based approach where missing values are replaced by multiple Bayesian draws from the conditional distribution of missing data given the observed data and covariates, creating multiple completed data sets.

Missing values will be imputed simultaneously based on an underlying joint normal distribution and using a Markov Chain Monte Carlo (MCMC) method.

The imputations will be done separately for each treatment group including baseline IGA, geographical region, baseline EASI score as additional covariates.

The number of imputations will be set to 100, the seed for the random function will be set to 3892203 for this study. To generate the multiple imputed data sets, the SAS procedure MI can be used as follows:

The input data set should have one record per subject with baseline EASI score and IGA score as well as the variables to be imputed (e.g. changes from baseline in EASI, or post-baseline IGA score).

Programming notes:

- The SAS procedure MIANALYZE expects a variable called "\_IMPUTATION\_" which is generated by the MI procedure. It might be needed to set the SAS option "VALIDVARNAME=UPCASE" temporarily in the program before the MI call, this option should be reset after the MIANALYZE call to VALIDVARNAME=V6.
- In case there are no missings in one treatment group, the MI procedure does not impute any values. In this case the corresponding data need to be imputed manually outside PROC MI and added to the dataset <impdata>.

The imputed data are saved in data set <impdata>. The outcomes of interest, i.e. the EASI 50/75 response and IGA 0 or 1 response will be calculated, e.g. as follows:

The treatment differences for each imputed data set will then be evaluated by Logistic regression and ODDS ratio as described in Section 5.4.2.2. This analysis will be done by \_IMPUTATION\_ for the comparison to the placebo treatment group. The model should be estimating response probability = 1 by using DESECENDING option. Using the ESTIMATE

option in the GENMOD procedure and the ODS OUTPUT data set "Estimates" provides the estimate for the odds ratio and confidence intervals.

```
PROC GENMOD <option>;
CLASS <stratum> <treatment>;
MODEL <response> = <explanatory variables> / link=logit dist=bin type3;
BY <by-variables);

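### The SAP omits post-baseline EASI change from the imputation model for Week 16 IGA response, contrary to Protocol 9.4.3, and does not record the change; the likely effect is small

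*SAP*

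**What the plan says.** Protocol 9.4.3, for subjects whose data are missing for reasons other than confounding therapy, lack of efficacy or adverse event: "The MI model will include IGA categories from all visits from randomization up to Week 16 as well as all EASI score at baseline", followed by "absolute change from baseline EASI score for all visits from baseline up to Week 16".

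SAP 2.5.3, on the same endpoint: "The multiple imputation model will include IGA categories from all visits from randomization up to Week 16". It does not mention EASI.

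SAP 5.2.3, the general imputation appendix: "The imputations will be done separately for each treatment group including baseline IGA, geographical region, baseline EASI score as additional covariates". The only reference there to post-baseline EASI is in the description of the input data set, which holds baseline EASI and IGA "as well as the variables to be imputed (e.g. changes from baseline in EASI, or post-baseline IGA score"). EASI change and IGA appear as alternatives.

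SAP 2.6.8, for the other binary endpoints, is looser: "The multiple imputation model will include scores from all visits from randomization up to the time point of imputation". It does not say that IGA and EASI enter one model together.

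SAP Section 4 lists two changes from the protocol: no adjudication of confounding medication, and no MCP-Mod. The imputation model is not listed.

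**The concern.** IGA has five categories, and entry requires a score of 3 or 4. EASI runs from 0 to 72 and is scheduled at the same visits (Protocol Table 6-1). Two patients with the same IGA history can therefore differ a good deal in EASI. Missing-at-random given IGA history and baseline covariates is a stronger assumption than missing-at-random given EASI history as well. The data that would weaken it are already collected.

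The assumption carries some weight. SAP 2.5.1 sets data after other-reason discontinuations to missing, and SAP 2.5.4 reports more discontinuations by subject decision than expected. Under Protocol 5.6.5, subjects still in the study at early termination are treated as prematurely withdrawn, so any who were short of Week 16 would also be imputed. Supportive estimands 1 and 2 go further and set data after every discontinuation to missing, including those for lack of efficacy.

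Disclosure also matters. The SAP was finalised on 29 September 2020, after the May 2020 interim results. It flags other departures where they occur (2.3.2, 2.5.1, 2.5.2, 2.6.2, 2.6.6), but not this one.

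**Working it through.** **Step 1: the models side by side.**

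| Model content | Protocol 9.4.3 | SAP 2.5.3 with 5.2.3 |
|---|---|---|
| IGA at all visits to Week 16 | yes | yes |
| Baseline EASI | yes | yes |
| Absolute EASI change at all visits | yes | not named |
| Region | not named | yes |
| Fitted by arm | not stated | yes |

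The SAP model is therefore not IGA alone. What is lost is post-baseline EASI change.

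**Step 2: size.** The plan gives no figure for the imputation model, so there is none to reproduce. The inputs to a large-sample simulation (40,000 subjects per scenario) were:

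- From the documents: dropout of 15% or 25% (SAP 1.1, the all-reason planning assumption), and response of 10% to 30% (Protocol 9.8: 10% on placebo, at most 20 points more on ZPL389).
- Assumed: all dropout is imputed, an upper bound on that planning rate; within-visit IGA–EASI correlation of about 0.5 to 0.8; dropout log-odds of 0.5 or 1.0 per SD of the last observed EASI.
- Both models use joint-normal imputation with IGA history, baseline IGA and baseline EASI. One adds EASI change at each visit. Draws use EM estimates, and an imputed IGA below 1.5 counts as response. With entry IGA of 3 or 4, a score of 0 or 1 already meets the 2-point reduction.

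Selected results, in percent. Each model's cell gives the arm rate, then the rate among imputed subjects.

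| Complete-data rate | Correlation | Log-odds per SD | Dropout | True rate among missing | Without EASI change | With EASI change | Arm shift (points) |
|---|---|---|---|---|---|---|---|
| 20 | 0.83 | 0.5 | 15 | 12.7 | 20.3 / 14.4 | 20.1 / 13.5 | 0.13 |
| 20 | 0.72 | 1.0 | 15 | 8.4 | 20.6 / 12.7 | 20.4 / 11.1 | 0.24 |
| 20 | 0.72 | 1.0 | 25 | 9.4 | 21.5 / 15.6 | 21.1 / 13.9 | 0.42 |
| 30 | 0.71 | 1.0 | 25 | 15.6 | 31.7 / 22.4 | 31.2 / 20.4 | 0.49 |
| 30 | 0.51 | 1.0 | 25 | 19.2 | 31.4 / 24.7 | 30.7 / 22.1 | 0.64 |
| 30 | 0.71 | −1.0 | 25 | 47.3 | 25.6 / 29.9 | 26.2 / 32.0 | −0.52 |
| 10 | 0.70 | −1.0 | 25 | 20.4 | 8.1 / 12.9 | 8.4 / 13.9 | −0.25 |

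Over all scenarios with high-EASI dropout, the arm shift is 0.05 to 0.64 points and the shift among imputed subjects about 0.2 to 2.8 points. The last two rows show the sign reversing when low EASI drives dropout.

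**Step 3: arithmetic check.** Error in arm rate = share imputed × error among the imputed. In the fourth row, without EASI: 0.25 × (22.4 − 15.6) = 1.7, and 30.0 + 1.7 = 31.7. With EASI: 0.25 × (20.4 − 15.6) = 1.2, giving 31.2. Both agree with the table. By the same rule, each 10% of an arm imputed adds at most about 0.10 × 2.8 = 0.28 points.

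**Step 4: how much restoring EASI corrects.** Fourth row: (22.4 − 20.4)/(22.4 − 15.6) = 2.0/6.8, or 29% of the error among the imputed. Fifth row: 2.6/5.5, or 47%. Sixth row: 2.1/17.4, or 12%. In most high-EASI scenarios the protocol model also stays too high, because joint-normal imputation of a five-category score adds error of its own.

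**Step 5: the difference between arms.** Take arms at 30% and 20% response with the same mechanism (correlation about 0.7, log-odds 1.0). With 25% dropout in both, the shift in the difference is 0.49 − 0.42 = 0.07 points. With 25% in the first and 15% in the second, it is 0.49 − 0.24 = 0.25 points.

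**Step 6: can the small arms support the fuller model?** At the interim's 187 patients and 2:1:1:2:2 allocation, a low-dose arm has about 187/8 ≈ 23 patients. Six post-baseline IGA values, baseline IGA and baseline EASI make 8 variables, with 8 × 9/2 = 36 covariance terms. Adding six EASI changes makes 14 variables, with 14 × 15/2 = 105 terms, before region is counted.

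**The case against.** The strongest reply is that omission is inferred. SAP 2.5.3 states what the model includes without saying that nothing else enters. SAP 5.2.3 imputes values simultaneously under a joint normal model and derives both EASI and IGA responses from one imputed data set, which a joint IGA/EASI model would also allow. The PROC MI code that would settle it does not appear in the text available for review, which may be a loss in reading the PDF. This stands as a caution. If that code contains EASI change for the IGA endpoint, the remedy is to say so in 2.5.3. As the prose reads, EASI change is not in the IGA model.

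Second, many patients with poor EASI never reach imputation. Discontinuations for lack of efficacy or adverse event are non-responders, and so are users of rescue or prohibited medication. Supportive estimand 3 counts every discontinuation as non-response, with subject-decision dropouts expressly in mind. This largely stands. It does not cover an IGA that was simply not recorded, which 2.5.3 also imputes.

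Third, a smaller model is defensible in arms of about 23. That is a fair reason, but the SAP does not give it, and fitting across arms would meet it.

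A reader might infer that the imputed response is simply too high, or that the omitted EASI data would put it right. Neither follows: the direction depends on who leaves, and Step 4 shows only partial correction. Another illustrative simulation, with 28% to 37% dropout, gave arm rates 0.7 to 1.4 points too high without EASI and at most 0.2 with it. That dropout exceeds the only rate in the documents, and the near-complete correction was not reproduced under the assumptions above.

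**Conclusion.** The discrepancy is real on the text and is unreported. Its numerical consequence is small. Under high-EASI dropout the extra bias is about 0.05 to 0.64 points per arm. At the upper end that is 0.0064 × 90 ≈ 0.6 of a responder in a planned arm of 90, against an assumed maximum effect of 20 points. Under low-EASI dropout the bias runs the other way, by 0.25 to 0.52 points in the two cases run. The net direction for ZPL389 versus placebo is not determined, because similar bias in both arms partly cancels and the documents do not show differential dropout.

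These sizes rest on assumed correlations and dropout dependence, and on 15% to 25% dropout with all of it imputed. The documents give neither the actual share imputed nor the final sample size.

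Because the SAP postdates the interim results, a reader might also infer that the model was changed in response to them. The documents show the timing but no motive. The trial was stopped for lack of efficacy and dose selection was abandoned, so a changed conclusion is unlikely. Severity: minor.

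**What to change.** Preferred: in SAP 2.5.3 and 5.2.3, add absolute EASI change at each post-baseline visit to the IGA imputation model, alongside IGA history, baseline IGA, baseline EASI and region. Fit it across arms with treatment as a covariate, so that the low-dose arms can support it. Pooling goes beyond Protocol 9.4.3, which does not say how arms are handled, and it assumes a common covariance across arms; the SAP should state both.

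Alternative: keep the reduced model, list it with a reason in SAP Section 4, and run the protocol model as a sensitivity analysis.

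Either way, no new data are needed, and the cost is a few lines in the imputation program and a sentence or two in the SAP. The downside of the preferred option is more variables in the model, with the pooling assumption that this brings.

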## 2.5.4 Supportive analyses

Supportive analyses for the primary estimand will focus on different methods of handling data in the cases of intercurrent events.

The following supportive estimands will be considered:

## Supportive estimand 1:

Population: Same as for the primary estimand

**Endpoint:** IGA response at week 16, where IGA response is defined as an IGA score of 0 or 1 with at least a 2 point improvement compared to baseline and no use of confounding therapy before the assessment time point.

Novartis	For business use only	Page 21
SAP		CZPL389A2203

**Treatment of interest:** the randomized treatment (ZPL389 or placebo) plus medications as allowed by the protocol but with no further treatment for patients who discontinue study treatment due an AE or lack of efficacy.

#### Handling of remaining intercurrent events:

• Treatment discontinuations for any reason: set data after discontinuation to be missing

The summary measure: difference in response rates between ZPL389 and placebo.

This estimand is considered since the classification of all patients who discontinue due to lack of efficacy or AE as non-responders in terms of IGA response may be too extreme. It is possible that patients experience improvement in their skin symptoms, but no improvement in another symptoms of their disease (such as itching) and for that reason discontinue study treatment. In this case, setting IGA response to non-response may not reflect what was happening to the patient. This supportive estimand will therefore help to assess whether the assumption that discontinuing the study due to lack of efficacy or AE implies lack of response on IGA is a reasonable assumption.

#### Supportive estimand 2:

Population: Same as for the primary estimand

**Endpoint:** IGA response at week 16, where IGA response is defined as an IGA score of 0 or 1 with at least a 2 point improvement compared to baseline. Any use of confounding treatment is ignored.

**Treatment of interest:** the randomized treatment (ZPL389 or placebo) plus medications as allowed by the protocol and further treatment taken to treat atopic dermatitis.

#### Handling of remaining intercurrent events:

• Treatment discontinuations for any reason: set data after discontinuation to be missing

The summary measure: difference in response rates between ZPL389 and placebo.

This estimand is considered to address the question of whether ZPL389 plus other medication as needed is more effective that placebo plus other medication as needed.

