If discontinuation of study treatment occurs, the subject should not receive additional doses. Subjects should remain in the study and be followed at least until the adverse event resolves / stabilizes, or until the end of the study, whichever is longer. I.e. After study treatment discontinuation, the subject should remain in the study and attend study visits as normal in Table 6-1 (without contacting IRT /drug dispensing). Subjects who discontinue treatment and wish to discontinue the study should at a minimum return for the End of Treatment visit (Week 16 visit) and the Follow up visit (Week 20 visit), as detailed in Table 6-1, and assessment should be completed and recorded in the appropriate CRF. The investigator must determine the primary reason for the subject's premature discontinuation of study treatment and record this information on the CRF.

The investigator must also contact the IRT to register the subject's discontinuation from study treatment.

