## Supportive estimand 4:

**Population:** Adult moderate to severe atopic dermatitis patients as defined by the study inclusion and exclusion criteria who were randomized to treatment, and not mis-randomized in the IRT. This implies that analyses will be based on the full analysis set.

Endpoint: Percentage change from baseline in EASI scores at week 16.

**Treatment of interest:** the randomized treatment (ZPL389 or placebo) plus medications as allowed by the protocol but with no further treatment for patients who discontinue study treatment.

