#### Handling of remaining intercurrent events:

• No intercurrent events are considered.

The summary measure: difference in means between ZPL389 and placebo.

# 2.6.5 Efficacy over time up to week 16

The principles laid out for the primary estimand will be followed in calculating the summary measures for each endpoint at each time point.

The underlying clinical question in general is: What is the effect of the study treatment versus placebo on the endpoint at each week, in patients with moderate or severe atopic dermatitis, who do not use confounding therapy that may affect their AD or the assessment of it, regardless of their use of protocol-allowed concomitant medicatons, and who have received the full intended duration of treatment at that timepoint?

Other questions that may have been of interest in the case of an effective treatment, such as when is a treatment effect first seen, or how long is the treatment effect maintained for, will not be addressed.

The main secondary estimands are described by the following attributes:

**Population:** Adult moderate to severe atopic dermatitis patients as defined by the study inclusion and exclusion criteria who were randomized to treatment, and not mis-randomized in the IRT. This implies that analyses will be based on the full analysis set.

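### Supportive estimand 2 counts further atopic dermatitis treatment as part of the regimen, but discards every outcome recorded after study drug is stopped

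*SAP*

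**What the plan says.** **Supportive estimand 2 (SAP 2.5.4).** The stated question is "whether ZPL389 plus other medication as needed is more effective that placebo plus other medication as needed". The treatment of interest is randomized treatment "plus medications as allowed by the protocol and further treatment taken to treat atopic dermatitis". The endpoint is IGA response at Week 16, and "Any use of confounding treatment is ignored". For stopping study drug the rule is "Treatment discontinuations for any reason: set data after discontinuation to be missing".

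**What happens to the missing values.** Under SAP 2.5.3, "the IGA score will be imputed using multiple impuation methods", using IGA categories from all visits up to Week 16. SAP 5.2.3 adds that imputation is done separately in each treatment group, with baseline IGA, region and baseline EASI as covariates.

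**Reuse.** SAP 2.6.1 applies the primary and all three supportive estimands to EASI50 and EASI75 response. SAP 2.6.5 extends three supportive estimands to efficacy over time.

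**Supportive estimand 4 (SAP 2.6.2, percent change in EASI).** The treatment of interest is described "with no further treatment for patients who discontinue study treatment". The rule is "No intercurrent events are considered". The stated question concerns treatment for up to 16 weeks with confounding medication permitted.

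**Data collection.** Protocol 5.6.2: "After study treatment discontinuation, the subject should remain in the study and attend study visits as normal in Table 6-1".

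**The concern.** The treatment clause in estimand 2 appears to be a deliberate change. The primary estimand and supportive estimands 1 and 3 all specify no further treatment for patients who stop because of an adverse event or lack of efficacy. Estimand 2 replaces that clause with one that brings further atopic dermatitis treatment in. Read in parallel, the new clause covers therapy taken after study drug is stopped. The data rule then removes exactly the outcomes that would show the effect of that therapy.

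If the two are left as they stand, the study report would present an analysis labelled as other medication as needed which, for discontinuers, estimates a continued-treatment effect. A reader could also set it beside estimand 4 for EASI, which uses recorded data, and take the two as answering the same kind of question.

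**Working it through.** The plan states no figure on this point, so the check is a comparison of the rules, followed by an illustration.

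**Step 1. How each Week 16 estimand treats outcomes after study drug is stopped**

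| Estimand | Confounding therapy | After discontinuation |
|---|---|---|
| Primary (IGA; also EASI50/75) | Non-response | Non-response if stopped for adverse event or lack of efficacy; otherwise missing, imputed |
| Supportive 1 | Non-response | Missing, imputed |
| Supportive 2 | Ignored | Missing, imputed |
| Supportive 3 | Non-response | Non-response |
| Main EASI % change | Later data missing | Missing, handled by MMRM |
| Supportive 4 (EASI % change) | Not handled, so recorded data used | Not handled, so recorded data used |

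Two things follow. Estimand 2 has the same discontinuation rule as estimand 1 and differs in its data only in how it treats confounding therapy. And no row for a binary endpoint uses an observed post-discontinuation value. That estimand 4 uses all recorded data is inferred from its rule and from SAP 2.6.2, which says the protocol included all data as recorded; it is not stated outright.

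**Step 2. What estimand 2 then targets.** Because all later values are blanked, the imputation model can learn only from on-treatment data in the same arm. Values after rescue or other therapy taken while on study drug stay in. The target is therefore the effect of randomized treatment plus other medication, had randomized treatment continued.

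**Step 3. How many patients could be involved.** SAP 1.1 gives an assumed core-study discontinuation rate of 15% to 25%, used to size the extension:

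- planned sample: 0.15 × 360 = 54 to 0.25 × 360 = 90
- interim sample: 0.15 × 187 ≈ 28 to 0.25 × 187 ≈ 47

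**Step 4. Illustration of the two targets.** Let pA and pP be the on-treatment response rates, dA and dP the discontinuation rates, and rA and rP the response rates after stopping. Assume that imputation returns the on-treatment rates.

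- Data set to missing: difference = pA − pP
- Recorded data used: difference = [(1 − dA)pA + dA·rA] − [(1 − dP)pP + dP·rP]

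Take pP = 10% and pA = 30%, the planning values in SAP section 3 (placebo 10%, maximum effect 20 points). With equal d and equal r the terms in r cancel:

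- set to missing: 30 − 10 = 20 points
- recorded, d = 15%: 0.85 × 20 = 17 points
- recorded, d = 25%: 0.75 × 20 = 15 points

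With dA = 15%, dP = 25% and a common r:

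- 0.85 × 30 + 0.15r − 0.75 × 10 − 0.25r = 18 − 0.10r
- this runs from 18 points at r = 0% to 13 points at r = 50%

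**Step 5. Direction.** Recorded minus missing = dA(rA − pA) − dP(rP − pP). This can take either sign. For example, with d = 15% in both arms, rA = 50% and rP = 10%, it is 0.15 × 20 − 0.15 × 0 = +3 points.

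**The case against.** A fair defence of estimand 2 runs as follows. A patient who has stopped ZPL389 is no longer on ZPL389 plus other medication. Keeping data after on-treatment rescue, which Protocol 5.5.6 allows after Week 4, while treating discontinuation hypothetically is a coherent strategy. Imputation conditions on the patient's own earlier IGA scores, so someone who stopped for lack of efficacy is not simply given a completer's result. The 15% to 25% is a planning assumption, and the SAP already reports that the interim analysis showed no treatment effect. Nor is it known how many Week 16 values exist: patients may withdraw consent, and Protocol 5.6.5 handles early study termination as premature withdrawal.

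Most of this stands, and it limits the point. It does not explain why estimand 2 adds further treatment exactly where its sister estimands exclude it after discontinuation. Nor does the SAP say that continued treatment is the target.

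A reader might infer more than the documents support:

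- **That neither estimand answers its question.** Estimand 2 answers a hypothetical version of its question. Estimand 4's data rule fits its question; only its treatment wording is at odds, and if that wording means no further study drug, little conflict remains.
- **That effects are overstated by 20/17 = 1.18 to 20/15 = 1.33.** This needs equal discontinuation, equal off-treatment response and imputation that ignores individual history. Topical therapy after stopping could also raise observed response above the imputed values.
- **That Table 5-1 shows topical therapy is allowed after early discontinuation.** The relevant cell is too broken in the available text to rely on, and the point does not need it.

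**Conclusion.** The point holds for supportive estimand 2 and for its EASI50, EASI75 and over-time versions: the treatment attribute and the discontinuation rule do not match, and the SAP does not say which one governs. As written, the analysis reflects other medication taken on study drug and a hypothetical continued-treatment outcome for those who stop. For the binary endpoints, outcomes that the protocol asks sites to collect after discontinuation are used in no estimand.

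The gap of 20 against 17 or 15 points shows only that the two rules estimate different things under the stated assumptions. Its size and direction in this trial cannot be derived from the documents, and with no treatment effect it may be close to zero. The primary estimand is untouched, and nothing here changes the conclusion of a trial stopped for lack of efficacy. The estimand 2 repair is worth making; the estimand 4 change is editorial.

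**What to change.** **Supportive estimand 2, with its EASI50/75 and over-time versions.** Replace the discontinuation rule so that the IGA or EASI recorded at the visit is used whether or not study drug has been stopped, and impute only where no assessment was recorded, for example after withdrawal of consent or early study termination. Reporting by arm how many discontinued patients have a recorded Week 16 assessment would show how much of the result is observed.

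**Alternative.** If the continued-treatment effect is what is wanted, say so in the question and limit further treatment to the period on study drug. This needs no rerun.

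**Supportive estimand 4.** Remove the clause excluding further treatment and state that all recorded data are used, including data after discontinuation and after confounding medication. This is wording only.

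**Cost.** A few SAP sentences and, for the first option, one rerun on data the protocol already collects. The imputation model for the remaining gaps should be restated, because post-discontinuation values would now enter it.
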